6.1 Specification of Safety Parameters

6.1.1 Definition of Adverse Events (AE)

An **adverse event** (AE) is any symptom, sign, illness or experience that develops or worsens in severity during the course of the study. Concurrent illnesses or injuries acquired during the course of the study should be regarded as adverse events. Abnormal results of diagnostic procedures are considered to be adverse events if the abnormality:

- results in study withdrawal
- is associated with a serious adverse event
- is associated with clinical signs or symptoms
- leads to additional treatment or to further diagnostic tests
- is considered by the investigator to be of clinical significance

CONFIDENTIAL

This material is the property of the NYU School of Medicine and Langone Medical Center. Do not disclose or use except as authorized in writing by the study sponsor

Interventional Template Version: 28 APR 2017

6.1.2 Definition of Serious Adverse Events (SAE)

Serious Adverse Event

Adverse events are classified as serious or non-serious. A **serious adverse event** is any AE that is:

- fatal
- life-threatening
- requires or prolongs hospital stay
- results in persistent or significant disability or incapacity
- a congenital anomaly or birth defect
- an important medical event

Important medical events are those that may not be immediately life threatening, but are clearly of major clinical significance. They may jeopardize the subject, and may require intervention to prevent one of the other serious outcomes noted above. For example, drug overdose or abuse, a seizure that did not result in in-patient hospitalization, or intensive treatment of bronchospasm in an emergency department would typically be considered serious.

All adverse events that do not meet any of the criteria for serious should be regarded as **non-serious adverse events**.

6.1.3 Definition of Unanticipated Problems (UP)

Unanticipated Problems Involving Risk to Subjects or Others

Any incident, experience, or outcome that meets all of the following criteria:

- Unexpected in nature, severity, or frequency (i.e. not described in study-related documents such as the IRB-approved protocol or consent form, the investigators brochure, etc)
- Related or possibly related to participation in the research (i.e. possibly related means there is a reasonable possibility that the incident experience, or outcome may have been caused by the procedures involved in the research)
- Suggests that the research places subjects or others at greater risk of harm (including physical, psychological, economic, or social harm).

This definition could include an unanticipated adverse device effect, any serious adverse effect on health or safety or any life-threatening problem or death caused by, or associated with, a device, if that effect, problem, or death was not previously identified in nature, severity, or degree of incidence in the investigational plan or application (including a supplementary plan or application), or any other unanticipated serious problem associated with a device that relates to the rights, safety, or welfare of subjects (21 CFR 812.3(s)).

6.2 Classification of an Adverse Event

6.2.1 Severity of Event

For AEs not included in the protocol defined grading system, the following guidelines will be used to describe severity.

- **Mild** – Events require minimal or no treatment and do not interfere with the participant's daily activities.
- **Moderate** – Events result in a low level of inconvenience or concern with the therapeutic measures. Moderate events may cause some interference with functioning.
- **Severe** – Events interrupt a participant's usual daily activity and may require systemic drug therapy or other treatment. Severe events are usually potentially life-threatening or incapacitating.

6.2.2 Relationship to Study Agent

The clinician's assessment of an AE's relationship to study agent (device) is part of the documentation process, but it is not a factor in determining what is or is not reported in the study. If there is any doubt as to whether a clinical observation is an AE, the event should be reported. All AEs must have their relationship to study agent

CONFIDENTIAL

This material is the property of the NYU School of Medicine and Langone Medical Center. Do not disclose or use except as authorized in writing by the study sponsor

Interventional Template Version: 28 APR 2017

assessed. In a clinical trial, the study product must always be suspect. To help assess, the following guidelines are used.

- **Related** – The AE is known to occur with the study agent, there is a reasonable possibility that the study agent caused the AE, or there is a temporal relationship between the study agent and event. Reasonable possibility means that there is evidence to suggest a causal relationship between the study agent and the AE.
- **Not Related** – There is not a reasonable possibility that the administration of the study agent caused the event, there is no temporal relationship between the study agent and event onset, or an alternate etiology has been established.

6.2.3 Expectedness

The study PI and Co-I [name] will be responsible for determining whether an AE is expected or unexpected. An AE will be considered unexpected if the nature, severity, or frequency of the event is not consistent with the risk information previously described for the study agent.

6.3 Time Period and Frequency for Event Assessment and Follow-Up

The occurrence of an AE or SAE may come to the attention of study personnel during study visits and interviews of a study participant presenting for medical care. All AEs including local and systemic reactions not meeting the criteria for SAEs will be captured on the appropriate RF. Information to be collected includes event description, time of onset, Co-I's assessment of severity, relationship to study product (assessed only by those with the training and authority to make a diagnosis), and time of resolution/stabilization of the event. All AEs occurring while on study must be documented appropriately regardless of relationship. All AEs will be followed to adequate resolution.

Any medical condition that is present at the time that the participant is screened will be considered as baseline and not reported as an AE. However, if the study participant's condition deteriorates at any time during the study, it will be recorded as an AE. UPs will be recorded in the data collection system throughout the study.

Changes in the severity of an AE will be documented to allow an assessment of the duration of the event at each level of severity to be performed. AEs characterized as intermittent require documentation of onset and duration of each episode.

The PI will record all reportable events with start dates occurring any time after informed consent is obtained until 7 (for non-serious AEs) or 30 days (for SAEs) after the last day of study participation. At each study visit, the investigator will inquire about the occurrence of AE/SAEs since the last visit. Events will be followed for outcome information until resolution or stabilization.

All unresolved adverse events should be followed by the investigator until the events are resolved, the subject is lost to follow-up, or the adverse event is otherwise explained. At the last scheduled visit, the investigator should instruct each subject to report any subsequent event(s) that the subject, or the subject's personal physician, believes might reasonably be related to participation in this study.

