7.4.3 Breaking the Study Blind

Study blind will be broken at the participation end visit.

8 Source Documents and Access to Source Data/Documents

The study case report form (CRF) is the primary data collection instrument for the study. All data requested on the CRF must be recorded. All missing data must be explained. If a space on the CRF is left blank because the procedure was not done or the question was not asked, write "N/D". If the item is not applicable to the individual case, write "N/A". All entries should be printed legibly in black ink. If any entry error has been made, to correct such an error, draw a single straight line through the incorrect entry and enter the correct data above it. All such changes must be initialled and dated. DO NOT ERASE OR WHITE OUT ERRORS. For clarification of illegible or uncertain entries, print the clarification above the item, then initial and date it.

Access to study records will be limited to IRB-approved members of the study team. The investigator will permit study-related monitoring, audits, and inspections by the IRB/EC, the sponsor, government regulatory bodies, and University compliance and quality assurance groups of all study related documents (e.g. source documents, regulatory documents, data collection instruments, study data etc.). The investigator will ensure the capability for inspections of applicable study-related facilities (e.g. pharmacy, diagnostic laboratory, etc.).

Participation as an investigator in this study implies acceptance of potential inspection by government regulatory authorities and applicable University compliance and quality assurance offices.

9 Quality Assurance and Quality Control

Quality control procedures will be implemented beginning with data entry on NYULH's REDcap system. Any missing data or data anomalies will be communicated to the site(s) for clarification/ resolution to ensure quality of data.

10 Ethics/Protection of Human Subjects

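### After the last visit, the only stated instruction asks for new adverse events that the participant or their own physician thinks related, which is narrower than the 7-day and 30-day recording windows

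*Combined protocol and SAP*

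**What the plan says.** Section 6.3 sets the recording period: "The PI will record all reportable events with start dates occurring any time after informed consent is obtained", running "until 7 (for non-serious AEs) or 30 days (for SAEs) after the last day of study participation". That sentence carries no relatedness condition, but 6.3 does not define what makes an event reportable.

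Active enquiry is tied to visits: "At each study visit, the investigator will inquire about the occurrence of AE/SAEs since the last visit". Sections 4.4, 5.3 and 16 schedule no visit, call or message after the last visit.

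For the time after the last scheduled visit, 6.3 has the investigator tell each participant to "report any subsequent event(s) that the subject, or the subject's personal physician" "believes might reasonably be related to participation in this study".

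Two other rules bear on this. Section 6.3 says that relationship to the study product is "assessed only by those with the training and authority to make a diagnosis". Section 6.2.2 says of the clinician's relationship assessment that "it is not a factor in determining what is or is not reported in the study", and asks that doubtful observations be reported.

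Section 7.2.4 compares adverse event rates with published literature, and 6.4.1 puts the study on hold if they exceed the usual literature rates. Section 7.4.3 adds: "Study blind will be broken at the participation end visit".

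**The concern.** The window and the instruction meant to fill it do not match. The window is defined by time and seriousness. The instruction is defined by believed cause. A participant who has a fall, a relapse or a hospital stay in the window and thinks it has nothing to do with the study has been given no reason to mention it.

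The filter also acts at the wrong point. Under 6.3 a trained person decides relatedness once the event is known. Under the instruction, someone outside the study team decides first, and an event they judge unrelated may never be assessed.

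At stake is the completeness of the safety count. Missed events make the observed rate look more favourable against the literature and make the hold in 6.4.1 less likely to be triggered.

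**Working it through.** The plan gives no figure for this point, so there is none to reproduce. The check has three parts.

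**1. The rules side by side**

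| Question | Recording window (6.3) | Last-visit instruction (6.3) |
|---|---|---|
| Which events? | Reportable events, no relatedness condition | Events believed related to participation |
| Who judges relatedness? | Trained persons with authority to diagnose | Participant or personal physician |
| Time limit? | 7 or 30 days | None stated |
| Active enquiry? | At study visits only | None |

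Section 6.2.2 also counts a temporal relationship as enough to call an event related. The participant is not told to use that test, so the two thresholds can differ for the same event.

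**2. How much calendar time the window covers**

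Assumptions: session 1 is on the baseline day; ten business days put session 10 on day 12, or on day 19 if the third week is used; Treatment End is 0 to 3 days later, so on day 12 to 22. Where the ActiGraph is used, 4.4 puts session 1 4 to 7 days after baseline, which extends the upper end to 22 + 7 = 29.

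Share = window / (days on study + window).

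- Treatment End as last visit, serious events: 30/(12 + 30) = 0.71 down to 30/(29 + 30) = 0.51.
- Treatment End as last visit, non-serious events: 7/(12 + 7) = 0.37 down to 7/(29 + 7) = 0.19.
- Optional follow-up as last visit, counted from session 10 as in 5.3.5 (21 to 35 days): earliest day 12 + 21 = 33, latest 19 + 35 + 7 = 61. Serious: 30/63 = 0.48 down to 30/91 = 0.33. Non-serious: 7/40 = 0.18 down to 7/68 = 0.10.

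The schedule in Section 16 places consent at screening. If that falls before baseline, all these shares are smaller. They are shares of time, not of risk.

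**3. What incomplete capture would do**

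Let p be the true proportion of participants with a new event in the window and q the probability that it reaches the study. Both are assumptions. With the 80 participants of 4.5, the expected number captured is 80pq, and the chance of seeing at least one is 1 − (1 − pq)^80.

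| p | q | Expected captured | P(at least one) |
|---|---|---|---|
| 0.02 | 1 | 1.6 | 0.80 |
| 0.02 | 0.5 | 0.8 | 0.55 |
| 0.02 | 0.25 | 0.4 | 0.33 |
| 0.05 | 1 | 4.0 | 0.98 |
| 0.05 | 0.5 | 2.0 | 0.87 |
| 0.05 | 0.25 | 1.0 | 0.63 |
| 0.10 | 1 | 8.0 | 1.00 |
| 0.10 | 0.5 | 4.0 | 0.98 |
| 0.10 | 0.25 | 2.0 | 0.87 |

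The direction is fixed: capture below 1 lowers the count. The amount depends wholly on p and q.

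**The case against.** **Other routes exist.** A reader might infer that unattributed events cannot reach the trial at all. The text does not support that. Section 6.3 also lets events come to light when a participant is interviewed while seeking medical care, many participants are patients of the site's MS centre (4.3), and weekly meetings review each participant's clinical course (Section 6). Events unresolved at the last visit are followed. This stands as a partial offset. But following open events does not find new ones, and the medical-care route is passive. Recruitment reaches across the continental United States (4.3) and includes people outside the centre (5.2.1), so care elsewhere may go unnoticed.

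**The attribution need not be a layperson's.** This is correct: the personal physician's belief is enough. That physician is still outside the study and is not shown to be the assessor in 6.3.

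**The rules may not collide.** The requirement to document events whatever their cause applies to events during the study, not expressly to the window. Section 6.2.2 speaks of the clinician's assessment. Reportable could mean reportable to the IRB, which 6.4.2 limits to related serious events. The instruction could be an open-ended safety net added to the windows. So this is a mismatch and an ambiguity rather than a flat contradiction. But the narrow reading of reportable fits poorly with a separate window for non-serious events, and if the instruction is only a safety net, nothing else solicits new events in the window.

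**The optional follow-up may cover part of it.** If the window runs from Treatment End, enquiry at a visit 4 ± 1 weeks after session 10 could pick up much of it. That visit is optional, and Section 16 does not mark adverse event reporting there, although 6.3 requires enquiry at every visit.

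**Bias between arms.** A reader might infer from 7.4.3 that sham participants will report less. The documents do not establish this. Section 7.4.3 does not say that participants are told their arm, nor which visit it means. The instruction refers to participation, which includes cycling in both arms. No test of adverse events between arms is planned. It remains a secondary possibility.

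**Conclusion.** The point holds as a mismatch between the recording window and the only stated way of soliciting new events in it. Followed as written, the instruction puts outside attribution ahead of trained assessment and probably under-counts new events after the last visit. The adverse event rates used in 7.2.4 and 6.4.1 are then biased downward.

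The size cannot be computed. The window is roughly half to seven-tenths of calendar time for serious events when Treatment End is the last visit, and less with the follow-up visit or a longer lead-in from consent. A reader might take that as the share of events lost. It is not: risk need not be uniform over time, and Section 6 describes the known device effects as ending once stimulation stops.

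The conclusion assumes that reportable is not limited to related events, and that no separate procedure document schedules contact in the window.

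**What to change.** In 6.3, replace the last-visit instruction with wording such as: *report every new or worsened event up to 7 days, and every serious event up to 30 days, after the last day of study participation, whether or not it is thought related; trained study staff assess relationship.* Keep the existing related-event instruction for anything later.

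The same edit should say what reportable means and which visit ends participation, so that the start of the windows is clear. Section 16 should be reconciled with 6.3 on adverse event enquiry at the follow-up visit.

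Optionally, send one scripted check at day 7 and one at day 30, using the e-mail or telephone contact that 4.6.2 already names for withdrawals.

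The cost is one sentence and the matching participant instruction, plus at most two short contacts per participant if the checks are adopted. The downside is a few more unrelated events to document.

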6.4 Reporting Procedures – Notifying the IRB

6.4.1 Adverse Event Reporting

Adverse event rates will be calculated and reviewed at DSMP meetings. Adverse event rates will be reported to the IRB as described previously. Should adverse event rates exceed the normal rates observed in the literature, the study PI will place the study on hold and review the safety of the study.

6.4.2 Serious Adverse Event Reporting

Serious adverse events that are related to the study device or interventions will be reported to the IRB within 24 hours of occurrence.

CONFIDENTIAL

This material is the property of the NYU School of Medicine and Langone Medical Center. Do not disclose or use except as authorized in writing by the study sponsor

Interventional Template Version: 28 APR 2017

6.4.3 Unanticipated Problem Reporting

Incidents or events that meet the OHRP criteria for UPs require the creation and completion of an UP report form. It is the site investigator's responsibility to report UPs to their IRB. The UP report will include the following information:

- Protocol identifying information: protocol title and number, PI's name, and the IRB project number;
- A detailed description of the event, incident, experience, or outcome;
- An explanation of the basis for determining that the event, incident, experience, or outcome represents an UP;
- A description of any changes to the protocol or other corrective actions that have been taken or are proposed in response to the UP.

To satisfy the requirement for prompt reporting, UPs will be reported using the following timeline:

- UPs that are SAEs will be reported to the IRB within 24 hours of the investigator becoming aware of the event.
- Any other UP will be reported to the IRB within five business days of the investigator becoming aware of the problem.
- All UPs should be reported to appropriate institutional officials (as required by an institution's written reporting procedures), the supporting agency head (or designee), and OHRP within five business days of the IR's receipt of the report of the problem from the investigator.

6.4.4 Reporting of Pregnancy

Participants that become pregnant during the course of the study will be discontinued from treatment and will be asked to complete a concluding participation end visit that includes no risk or involvement of treatment. Only assessment will occur at the participation end visit.

6.5 Study Halting Rules

There are no pre-defined rules for stopping the study. Individual participants may be removed from the study by the PI and/or Co-I.

6.6 Safety Oversight

It is the responsibility of the Principal Investigator to oversee the safety of the study at his/her site. This safety monitoring will include careful assessment and appropriate reporting of adverse events as noted above, as well as the construction and implementation of a site data and safety-monitoring plan. Medical monitoring will include a regular assessment of the number and type of serious adverse events by Co-I [name].

Safety and tolerance of study protocols will be assessed via safety reports after every ten participants that complete the study. Signed memos including the details of the reports will be submitted to the IRB in a timely fashion.

7 Statistical Considerations

7.1 Statistical Hypotheses

Research hypothesis

There is a significant difference between active and sham groups by comparing primary and secondary outcomes at baseline and end treatment time.

Null hypothesis

There will not be a significant difference between active and sham groups

CONFIDENTIAL

This material is the property of the NYU School of Medicine and Langone Medical Center. Do not disclose or use except as authorized in writing by the study sponsor

Interventional Template Version: 28 APR 2017

7.2 Description of Statistical Methods

7.2.1 General Approach

Study design of the study is a double- blind randomized controlled trial.

The primary, secondary outcomes and demographic variables will be examined with summary statistics, including means, medians, standard deviations (SD), minimum, and maximum values for continuous variables, and frequencies and proportions for categorical variables.

The characteristics of the participants in the two groups will be compared at baseline using two- sample t-tests for continuous variables and the chi-square test for categorical variables.

The Shapiro-Wilk test will be performed, histograms will be constructed, and measures of central tendency and dispersion will be calculated to test the assumption that distribution is normal. If the normality check will fail, a transformation of the data will be done as corrective procedures.

The general approach of statistical analyses will be a repeated-measures analysis of variance (RM-ANOVA) with tDCS (2 levels: Active and Sham) as the between-independent variable and Time (3 levels: Day 1, Day 10, and after 4-weeks) as the within-independent variable.

In the inferential tests statistical significance will be set at 5% and all p-values is two-sided.

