3.4 Study Endpoints

3.4.1 Primary Study Endpoints

To determine the efficacy of the combination of tDCS and physical training, the following primary outcome measures have been chosen:

- Efficacy measured by comparison between the active and sham conditions by comparing the changes in gait velocity and stride length at baseline and participation end
- Compliance measured by 80% of participants having completed the study sessions

CONFIDENTIAL

This material is the property of the NYU School of Medicine and Langone Medical Center. Do not disclose or use except as authorized in writing by the study sponsor

Interventional Template Version: 28 APR 2017

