4.9 Study Procedural Intervention Description

4.9.1 Administration of Procedural Intervention

Study technicians trained to oversee tDCS sessions will administer the tDCS treatments. Training includes familiarity with the device and all of its safety features. Furthermore, technicians will be trained to properly oversee the physical activity sessions to ensure a safe environment.

Procedure for the administration of the treatment:

Electrodes preparation: the $5 \times 5 \text{ cm}^2$ carbon rubber electrodes work with saline solution in order to increase conductance. Inject 5 ml of saline solution on the external surface of the carbon rubber of each electrode.

Electrodes montage: The carbon rubber sponge electrodes will be placed according to the International 10-20 EEG System. The anodal electrode will be attached at Cz position on the scalp, which corresponds to the lower limb motor cortex. The cathodal electrode will be attached at the supraorbital area on the forehead. Before starting stimulation session check the impedance. Study technicians will troubleshoot the connection if the impedance is high enough that the device cannot reliably stimulate.

Arm 1: Active tDCS and physical training

Participants will receive active tDCS while performing physical training (see detailed description in Section 6.3). A direct current of 2.5 mA will be applied throughout the stimulation session.

Arm 2: Sham tDCS and physical training

Participants will receive a sham tDCS while performing physical training (see detailed description in Section 6.3). During a sham session, the device is programmed to ramp up to the desired intensity (target 2.5 mA) and ramp down for the initial 60 seconds, with no current delivery during the session, and then again at the end of the session. These brief periods of stimulation serve to mimic the effects of a true stimulation session.

Schedule of the intervention procedure: 20 minutes of active/sham stimulation, once daily, scheduled for 10 business days over the course of approximately two weeks. The participant will be able to compensate for any missed session the week after to complete a total of 10 visits. The total duration of the treatment will be approximately 3.3 hours (20 mins x 10 sessions).

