5.3.4 Treatment End visit (within 3 days after session 10)

- Gait assessment with instrumented 10-meter walk (i-10MW), functional mobility assessment with instrumented Time Up and GO (i-TUG), Timed 25-Foot Walk (T25-FW), instrumented 2 minute walk (i-2MW) test, balance assessment with static posturography test, administration of Berg Balance Scale, and administration of questionnaires (9-item FSS, 21-item MFIS, MSWS-12, 54-MSQOL, and VAS- F 0-10)
- Cognitive assessment using BICAMS and CogState brief battery

5.3.5 Final Study Visit (within 4 ± 1 weeks from the end of treatment i.e. Session 10)

- Gait assessment with instrumented 10-meter walk (i-10MW), functional mobility with instrumented Time Up and GO (i-TUG), and balance assessment with static posturography test, administration of Berg Balance Scale, Timed 25-Foot Walk (T25-FW)
- Administration of questionnaires (9-item FSS, 21-item MFIS, MSWS-12, 54-MSQOL, and VAS- F 0-10)
- Record participant's adherence to treatment program
- Cognitive assessment using BICAMS and CogState brief battery
- Collect the ActiGraph device (Optional)

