7.2.2 Analysis of the Primary Efficacy Endpoint(s)

Gait speed and Stride length

- Continuous variable (repeated measure)
- The Shapiro-Wilk test will be performed: histograms will be constructed, and measures of central tendency and dispersion will be calculated to test the assumption that distribution is normal
- If normality check will fail a transformation of the data will be done as corrective procedures (transformation will be made according to data distribution)
- Repeated-measures analysis of variance (RM-ANOVA) with tDCS (2 levels: Active and Sham) as the between-independent variable and Time (3 levels: Day 1, Day 10, and After 4-weeks) as the within-independent variable. In the inferential tests statistical significance will be set at 5% and all p-values is two-sided.

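### The three-level RM-ANOVA relies on sphericity, which the plan neither checks nor corrects for, and the error term for the baseline-to-end comparison is left open

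*Combined protocol and SAP*

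**What the plan says.** - **Model.** Section 7.2.2 specifies for gait speed and stride length a "Repeated-measures analysis of variance (RM-ANOVA) with tDCS (2 levels: Active and Sham) as the between-independent variable", with Time at three levels as the within-subject factor. Section 7.2.1 gives this as the general approach: "Time (3 levels: Day 1, Day 10, and after 4-weeks) as the within-independent variable". Section 7.2.3 repeats it for the Timed Up and Go parameters, the sway parameters and the questionnaire scores.
- **Level.** "In the inferential tests statistical significance will be set at 5% and all p-values is two-sided".
- **Assumptions.** "If the normality check will fail, a transformation of the data will be done as corrective procedures". The normality step appears once in 7.2.1, once in 7.2.2 and three times in 7.2.3. Sphericity, an epsilon correction, a multivariate test and a covariance structure are not mentioned.
- **Question.** The primary efficacy endpoint in 3.4.1 is a between-arm comparison made by "comparing the changes in gait velocity and stride length at baseline and participation end". Section 7.1 frames the hypothesis as a difference between arms "by comparing primary and secondary outcomes at baseline and end treatment time".
- **Timing.** Treatment is given "once daily, scheduled for 10 business days over the course of approximately two weeks" (4.9.1). The last assessment follows about four weeks later (5.3.5).

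The plan does not say whether the arm, Time or interaction effect is the primary test.

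**The concern.** The univariate F test for treatment-by-Time has its stated size only if the three pairwise differences between visits have equal variance. There is reason to doubt that here. One visit precedes treatment and two follow it, and both arms do the cycling programme. People who respond differently to exercise will therefore differ in their later values but not at baseline, even if tDCS has no effect.

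The second issue is the comparison that the protocol actually asks about. A baseline-to-end contrast can be drawn from a three-level RM-ANOVA with its own error or with the pooled within-subject error. The pooled error averages over all three pairs of visits, so it may be too small or too large for this pair. The plan leaves that choice open. If it is made after the data are seen, the size of the primary test is not known in advance.

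**Working it through.** **Inputs.** Two arms, 1:1 (3.3). 80 enrolled less 10% dropout leaves 72 (4.5), so 72 / 2 = 36 per arm. Three time levels. Two-sided 5%. The documents give no correlations between visits, so every covariance below is an assumption. Visit variances are set to 1 except where stated.

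**Formulas.** Let V_BE, V_BF and V_EF be the variances of the within-person differences baseline-end, baseline-follow-up and end-follow-up. With unit variances each is 2(1 − r). Let V̄ be their mean.

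- Own error: the variance of the between-arm contrast is 2·V_BE/36, on 72 − 2 = 70 df.
- Pooled error: the within-subject mean square estimates V̄/2, so the same contrast is assigned variance 2·V̄/36, on 2 × 70 = 140 df.
- Approximate size with pooled error: 2·[1 − Φ(1.96 / √(V_BE/V̄))].
- Epsilon for the interaction test: (Σλ)² / (2Σλ²), where λ are the two non-zero eigenvalues of the centred covariance matrix.

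**The plan's own figure.** Under compound symmetry (r = 0.7 for every pair), V_BE = V_BF = V_EF = 0.6, the ratio is 1 and epsilon is 1. Simulation gives 5.0% for the uncorrected test, so the stated 5% is reproduced when sphericity holds, whatever the spacing of visits.

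**One pattern by hand.** Take correlations of 0.6 between baseline and each later visit, and 0.9 between the later two. Then V_BE = V_BF = 0.8, V_EF = 0.2 and V̄ = 1.8/3 = 0.6. The eigenvalues are 0.5 and 0.1, so epsilon = 0.36 / (2 × 0.26) = 0.69. The ratio is 0.8/0.6 = 1.33, so 1.96/√1.33 = 1.70 and the pooled size is about 9.0%.

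**Simulation.** No treatment effect, 36 per arm, 100,000 trials per row (Monte Carlo standard error about 0.07 percentage points). Correlations are in the order baseline-end, baseline-follow-up, end-follow-up.

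| Assumed pattern | V_BE/V̄ | Epsilon | Interaction, uncorrected | Interaction, GG | Contrast, own error | Contrast, pooled error | ANCOVA at end |
|---|---|---|---|---|---|---|---|
| Compound symmetry, 0.7 | 1.00 | 1.00 | 5.0% | 4.8% | 5.0% | 5.0% | 5.0% |
| Decay over days 0/14/42, 0.9 per 14 days | 0.53 | 0.78 | 5.9% | 4.8% | 4.9% | 0.8% | 4.9% |
| Same, 0.7 | 0.61 | 0.85 | 5.7% | 4.9% | 5.0% | 1.3% | 5.0% |
| Same, 0.5 | 0.71 | 0.91 | 5.3% | 4.8% | 5.1% | 2.2% | 5.0% |
| Baseline apart (0.8, 0.8, 0.9) | 1.20 | 0.86 | 5.6% | 4.8% | 5.0% | 7.3% | 5.0% |
| Baseline apart (0.6, 0.6, 0.9) | 1.33 | 0.69 | 6.7% | 5.0% | 5.1% | 9.1% | 5.0% |
| Follow-up apart (0.9, 0.6, 0.6) | 0.33 | 0.69 | 6.7% | 4.9% | 4.9% | 0.1% | 4.8% |
| End-visit variance doubled, 0.7 | 1.16 | 0.91 | 5.5% | 4.9% | 5.0% | 6.9% | 5.1% |
| Extreme: end apart (0.3, 0.999, 0.3) | 1.50 | 0.50 | 8.4% | 4.9% | 4.9% | 11.1% | 4.9% |

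A second run with different random numbers gave at most 6.9% for the uncorrected test at epsilon 0.69. Results at 19 per arm, the figure in 7.3, are similar.

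**Ceiling.** With three levels epsilon cannot fall below 0.5. At that bound the statistic behaves as F on 1 and 70 df but is compared with the 5% point of F on 2 and 140 df, about 3.06. The chance of |t| on 70 df exceeding √3.06 = 1.75 is about 8.5%.

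**The case against.** The strongest reply is that the question in 3.4.1 and 7.1 is a single-degree-of-freedom comparison of two arms on one change. With its own error term it needs no sphericity, and every row of the table shows about 5%. The plan nowhere specifies pooled error, and silence is not a choice of the worst option. This stands. A reader might infer that the baseline-to-end test must exceed 5%, and the documents do not support that.

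The direction with pooled error also depends on an unknown covariance. If people's responses to exercise differ and persist wholly, partly or not at all, V_BE exceeds V̄. To see this, write the response as R at end and kR at follow-up, with k between 0 and 1. The three differences then carry 1, k² and (1 − k)² times the response variance. These sum to at most 2, so their mean is below 1. If visit-to-visit drift dominates instead, baseline and end are the closest pair and the pooled test is conservative.

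Two other readings are tempting. One is that unequal spacing of visits (about 0, 2 and 6 weeks) is the cause. Time is a categorical factor, and equal difference variances give 5% at any spacing. The other is that a planned confidence interval is too narrow. The plan states none for a treatment contrast; its only 95% confidence wording describes the sway ellipse in 5.2.1.

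It is also fair to say that this is a pilot, that the likely excess in the interaction test is modest, and that an epsilon correction might be applied in practice without being written down. None of this settles which test is primary or which error term it uses.

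**Conclusion.** The point holds as a gap in the specification with a modest, conditional effect on size. The uncorrected treatment-by-Time test depends on sphericity, and at 36 per arm it runs at about 5.3% to 6.9% under the plausible non-spherical patterns examined. It cannot go much above 8.5%. The larger uncertainty is in the comparison that the protocol names: about 5% with its own error, but from about 1% or less to 9% or more with pooled error.

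The correlations are assumed throughout, and patterns close to spherical would give values close to 5%. The figures also assume normal data and complete values at all three visits, although the four-week visit is marked optional in 4.4 and section 16. The documents do not show that the stated 5% will be exceeded. They show that it is not secured.

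**What to change.** In 7.2.1 to 7.2.3:

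1. Name the primary test as the between-arm comparison at treatment end adjusted for baseline, either by ANCOVA on the treatment-end value or by a mixed model with unstructured covariance across the three visits. Either one targets the stated endpoint, and the ANCOVA held 4.8% to 5.1% in every pattern above.
2. Use the same approach for the secondary outcomes listed in 7.2.3.
3. If an omnibus Time or treatment-by-Time test is kept, state that it carries a Greenhouse-Geisser or Huynh-Feldt correction, and that single time contrasts use their own error term.

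The cost is a sentence or two of analysis text, using data already scheduled. The downside is slightly larger p-values for the omnibus tests. The change should be made before unblinded results are available.
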